2.5.2 Volumetric MRI

Screening (baseline) volumetric measurements are performed using FreeSurfer software. This leads to reference volumes for whole brain, ventricles, hippocampus, and intra-cranial.

Volumetric data will be available for the following regions:

- intra-cranial volume (ICV),
- total/whole brain,
- left/right hippocampus,
- lateral ventricles.

In order to assess atrophy rate, volumetric MRI images from follow-up timepoints are compared to those from screening, using the boundary shift integral (BSI) technique in selected brain regions. The technique determines the total volume through which the boundaries of a given cerebral structure have moved, and hence, it aims at quantifying the amount of change in these selected brain regions. The output of the method is a change from baseline in volume (atrophy).

Volume changes in the following regions of interest (ROI) will be reported:

- whole brain,
- hippocampus (sum of left and right),
- lateral ventricles (left and right).

Tables

Summary statistics for absolute change and percent change from Baseline to timepoint will be provided. All statistics will be based on the total volume, i.e. the sum of the respective left and right volumes as applicable. In addition, the annualized percentage change will be calculated as the mean of individual participant annualized percentage change (percentage change per participant / time interval (in days) between current MRI assessment and date of baseline MRI assessment per participant) x 365.25. Time interval (in days) will be derived as date of current MRI assessment – date of baseline MRI assessment + 1.

Raw volumes, as well as changes, % changes, and annualized % changes from baseline will be summarized by visit including TEC, EoS, and last assessment on treatment, last assessment off treatment.

For investigation of worsening (increased atrophy) under treatment and reversibility, these summary statistics will also be provided for the mSAF by visit including TEC, EoS, and last assessment on treatment, last assessment off treatment.

The relationship between percentage change from baseline in hippocampal and whole brain volumes and change in RBANS total score and APCC score will be examined through correlation analysis. This will be done for participants with at least 3 months exposure (mSAF). The Spearman and Pearson correlation coefficients and associated p-values will be reported.

2.5.3 Primary endpoint

There are two primary endpoint variables:

Time-to-event (TTE), with event defined as time to first confirmed diagnosis of MCI due to AD or dementia due to AD (whichever occurs first), and

Change in the API preclinical cognitive composite (APCC), from baseline to Week 260_(M 60)

Time to event (MCI due to AD or dementia due to AD)

Time-to-event (TTE), with event defined as the first confirmed diagnosis of MCI due to AD or dementia due to AD (whichever occurs first). An event is identified as a Progression Adjudication Committee (PAC)-confirmed diagnosis triggered either by an investigator diagnosis or an increase in the CDR global score. The confirmation by the PAC consists of two confirmed adjudications based on data from two consecutive visits.

In case of an identified event, TTE will be calculated as the time from randomization to the first confirmed diagnosis. For each event (confirmed diagnosis), the date of the initial investigator diagnosis will be used to establish the date of the event (neither the date of adjudication, nor the date of the confirmation). In case no confirmed event has been observed for an individual, the

observation will be censored, and the censoring date will be defined as the last date where the diagnosis classification has been assessed. Time to censoring date will be calculated from day of randomization.

The team agreed that the date of 25 August 2019 was the cut-off date/point for the final analysis. The final TTE analysis will include data until this cut-off point. Any data collected after this cut-off point will not be used for the primary analysis of TTE. That means specifically that only confirmed events collected up to the data cut-off point will be counted. Confirmation information collected after the cut-off point to confirm an earlier (meaning before the cut-off point) adjudicated diagnosis of MCI or AD due to dementia will not be taken into consideration. As a consequence, the observation will be censored at the last date prior to cut-off point that the TTE endpoint was evaluated, and the unconfirmed diagnosis will not be counted as an event in the primary analysis.

Due to the early termination of the studies, only a small number of events following the above definition have been observed. Hence, for the abbreviated CSR, the number (%) of participants meeting the following additional situations (change in diagnosis classification) will also be reported:

1. Participants with a change in diagnosis classification from cognitively unimpaired by the principal investigator at any time
 - MCI due to AD,
 - MCI not due to AD,
 - Dementia due to AD,
 - Dementia not due to AD.
2. Participants with an increase in CDR global score from baseline at any time (any increase, increase less than 1, increase of 1 or more);
3. Participants where data was sent for adjudication to PAC (regardless of confirmation at the following visit) split by the result of the adjudication:
 - Cognitively unimpaired,
 - MCI due to AD,
 - MCI not due to AD,
 - Dementia due to AD,
 - Dementia not due to AD,
 - Other (Unable to adjudicate, data not collected, not known).

Note that cut-off date/point (25 August 2019) used for protocol defined event (MCI due to AD or dementia due to AD) will not be applicable for the above defined additional situations. Data up to the the database lock date will be used for the analysis of these additional situations.

APCC score

The APCC test score is defined as a weighted sum of the following test items:

Raven's Progressive Matrices – subset items A2, A4, A8 & B1-B6 (0-9)

MMSE:

- Orientation to Time (0-5)
- Orientation to Place (0-5)

RBANS (Subtest raw scores):

- List Recall (0-10)
- Story Recall (0-12)
- Coding (0-89)
- Line Orientation (0-20)

The range of the APCC test score is from 0 to 100 where higher scores in the APCC correspond to a better cognitive performance. The APCC will be derived based on the test items using the below formula and weights:

APCC test score = $1.360 \times \text{RBANS List Recall} + 1.100 \times \text{RBANS Story Recall} + 1.390 \times \text{Raven's Progressive Matrices (subset items A2, A4, A8, B1-B6)} + 0.321 \times \text{RBANS Coding} + 0.510 \times \text{RBANS Line Orientation} + 2.140 \times \text{MMSE Orientation to Place} + 2.240 \times \text{MMSE Orientation to Time}$.

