2.5.5 Handling of missing values/censoring/discontinuations

Time to event (MCI due to AD or dementia due to AD), Time to first change in diagnosis classification and Time to first decrease in RBANS total \geq 14 points

In general, an observation will be censored if no event has been observed at the TTE analysis cut-off date. The censoring date will be defined as the last date (before cut-off date) where the TTE endpoint has been assessed.

The censoring date for each participant that did not have an event (i.e., a confirmed diagnosis) is defined as follows:

1. For participants ongoing in the study without a confirmed diagnosis at the time of the cut-off: the last day of a diagnosis assessment (the previous visit where a diagnosis assessment occurred prior to the cut-off date).
2. For participants who permanently discontinued from the study prior to the cut-off: The last day of a diagnosis assessment prior to study discontinuation.
3. For participants who had their last diagnosis assessment prior to randomization (i.e. during screening epoch) or do not have any diagnosis assessment post randomization, their randomization date will be used as censoring date.
4. For analysis of time to first decrease in RBANS \geq 14 points, the last RBANS assessment date will be used as censoring date instead of last diagnosis assessment date mentioned in above three points.

Note: For Time to MCI due to AD or dementia due to AD, the cut-off date will be 25 August 2019. Analysis of Time to First change in diagnosis classification, the cut-off date will be database lock date, additional analysis of time to first change in diagnosis classification will be performed for participants on treatment. Also time to first decrease in RBANS \geq 14 points will be performed for participants on treatment.

Further details on derivation of events and censoring will be added to the programming document specifications (PDS).

Other primary efficacy endpoint variable (APCC)

Due to the early termination of the trial, analyses of primary efficacy variable APCC will in general be based on observed cases only, i.e. there will be no imputation of missing data. Exception in primary efficacy variable APCC applies to missing data in subtests of Raven's matrices included in the primary efficacy variable APCC. Missing values for the subtests of Raven's matrices of the APCC may be imputed using the imputation rule defined in [Appendix 5.1.3.3.1](#).

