2.14 Interim analysis

Due to early termination of the studies, the planned IA for CNP520 will not be performed.

3 Sample size calculation

A total of up to 2000 participants will be randomized into the study, with a sample size of 800 for the selected dose of CNP520 and placebo, respectively, thereby achieving a 1:1 ratio for the selected CNP520 dose vs placebo. Sample size calculations were mainly based on reaching a target power of 80% for the test of the elementary hypothesis on the TTE endpoint for the selected dose of CNP520 vs placebo.

Type I Error Rate and Power

The overall significance level will be $\alpha=5\%$ (rate of any false positive decision, i.e., at least one Null-Hypothesis is rejected although all were true). The overall α of 5% will be split between the two primary hypotheses on the two primary endpoints as follows: An alpha of 4% will be chosen to test the hypothesis H₀₁ on the time to first diagnosis of MCI or dementia due to AD; an alpha of 1% will be chosen to test the hypothesis H₀₂ on the APCC score.

A small portion (0.004% and 0.001%, respectively) of the error rates will be spent in a Bonferroni split to account for multiplicity due to the IA on primary endpoints. Since the portion will be very small, this has been ignored for power calculations.

Sample size calculations were mainly driven by power considerations for the primary endpoint time to first diagnosis of MCI or dementia due to AD, based on the planned recruitment time of two years and variable observation period of five to seven years. The power, i.e., the probability to detect a true difference between treatment arms, was set to be at least 80% for this analysis.

The power for the primary analysis does not account for the potential and non-negligible inflation of the type II error due to futility analyses using biomarkers and the primary efficacy endpoints. On the other hand, the potential inflation of the type II error due to the adaptive design is expected to be minimal and hence, has been ignored for the calculations of sample size.

Simulations

The sample size of the trial has been calculated based on simulations. Further details are described in the Sample Size documentation.

Sample Size Calculation based on the Primary Endpoint Time to MCI / Dementia due to AD

The sample size calculation for the TTE endpoint, i.e., for time to first diagnosis of MCI due to AD or dementia due to AD has been based on the following assumptions:

two years accrual period,

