
five to seven years observation period,

30% of participants experiencing an event in the control group in 60 months observation period,

a hazard ratio of 0.75 in favor of the active treatment arm,

30% drop-out rate over 60 months (corresponding to a yearly drop-out rate of about 6.9%),
 $\alpha = 4\%$, two-sided test.

Power has been investigated for the comparison of the CNP520 high dose versus placebo using a log-rank test under Lakatos approximation. Based on the above-mentioned assumptions, a sample size of 1600 participants (800 participants in the selected CNP520 dose group and placebo, respectively) need to be randomized to achieve at least 80% power. The targeted number of events required to be observed in the active treatment arm is 180 and that placebo group is 228 adding up to a total of 408 target events for the comparison of the primary active arm versus placebo. Assuming the same underlying event rate of 22.5% in the active treatment arms, the targeted number of events in the secondary active arm is calculated as 22.5% of the total number of participants in the arm (i.e. 90 events). Supposing therefore that no adaptation occurred (i.e. 2000 participants randomized), the overall targeted number of events is 498 (= 228 + 180 + 90). The power estimation using the log-rank test provides a conservative estimate and should thus be interpreted as the lower limit of power.

In the simulation setting, the trial data were simulated using models which included certain prognostic factors. This enabled the investigation of different population assumptions and allowed each subject to have its own TTE distribution depending on baseline characteristics. The power estimates based on the adjusted Cox PH model hence were overly optimistic and should be interpreted as the upper limit of power which may only be reached in a best case scenario. Power for the TTE endpoints reached 89% and more in simulations depending on the underlying assumptions on the population.

The above calculation was done using the commercial software PASS 2008.

Power calculations based on the primary endpoint APCC

Power considerations for the APCC have been based on the MMRM model generated from the simulated trials and on standard power calculation based on a t-test. The following assumptions for the power calculations based on the change from baseline to Week 260_(M 60) in APCC were used:

- Statistical test used: t-test (standard) and MMRM (simulations),

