5.4.1 Primary analysis

Kaplan Meier approach for TTE

The Kaplan-Meier estimates of the survival functions for each treatment will be plotted. The plot will include the number of participants at risk for each treatment group at pre-specified timepoints. Median time to event and quartiles including 95% confidence intervals, if estimable, will be provided for each treatment group using the SAS procedure LIFETEST. The confidence intervals will be based on log-log transformation. For each treatment group and time interval: participants at risk, participants with event, participants with event divided by participants at risk, cumulative participants with event and cumulative event probability including 95% confidence interval will be provided.

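### Confirmed-event Kaplan-Meier rates are biased downward after early termination, because non-events stay at risk at a last visit where no event can be counted

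*SAP*

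**What the plan says.** SAP 2.5.3 defines the event as an adjudicated diagnosis: "The confirmation by the PAC consists of two confirmed adjudications based on data from two consecutive visits". Protocol 6.3.1 puts the confirming visit six months after the one that triggered adjudication. The event is dated at the initial diagnosis. Confirmation that arrives after the cut-off is ignored, and then "the observation will be censored at the last date prior to cut-off point that the TTE endpoint was evaluated".

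SAP 2.5.5 applies the same date to participants without an event who are still in the study at the cut-off. For those who left, the censoring date is "The last day of a diagnosis assessment prior to study discontinuation". Anyone with no post-randomisation diagnosis assessment is censored at randomisation.

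SAP 2.5.4 treats everyone in the study without an event as at risk and runs the analysis if at least five events occurred. SAP 5.4.1 promises, by arm and time interval, "cumulative event probability including 95% confidence interval will be provided".

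**The concern.** The numerator needs two visits and the denominator needs one. A participant whose only post-baseline diagnosis assessment is at month 6 counts in the month-6 risk set with no chance of being an event there. The same holds at the final visit of every non-event.

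The rule comes from the protocol (9.4.1 to 9.4.3), where follow-up of five to seven years makes one unconfirmable visit a small part of the total. After the July 2019 stop, SAP 2.5.4 notes that hardly anyone had data on active treatment past one year, so that visit is now a large part. SAP 2.5.3 puts the small number of events down to early termination and does not mention the censoring rule.

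At stake are the absolute progression rates for the protocol-defined primary endpoint. The 95% intervals reflect sampling error only and cannot cover this bias.

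**Working it through.** **The plan's own figure.** The documents state no size for this bias. The event target can be reproduced: with "a hazard ratio of 0.75 in favor of the active treatment arm", two-sided alpha 4% and 80% power, 4(2.054 + 0.842)² / (ln 0.75)² gives 406 events against the stated 408. The target is not at fault.

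**Inputs**
- SAP Section 3: "30% of participants experiencing an event in the control group in 60 months observation period". Taken as exponential, the risk per six months is q = 1 − 0.70^(6/60) = 3.50%, and the true 12-month risk is 1 − 0.70^(12/60) = 6.89%.
- SAP Section 3: 30% drop-out over 60 months, so six-month retention is 0.70^0.1 = 0.965.
- Protocol 6.3.1: six-monthly assessments, with confirmation at the next one.
- Follow-up at the cut-off: not given, so assumed and varied.

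**Formula.** Let L be a participant's last assessment. A first diagnosis at visit k counts only if visit k+1 exists, so the Kaplan-Meier hazard at visit k is q × r(k), where r(k) = P(L ≥ k+1) / P(L ≥ k). The relative loss is driven by r(k) and hardly depends on the 30% assumption.

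**Worked case: follow-up uniform on 0 to 24 months**
- r(1) = (0.50/0.75) × 0.965 = 0.643; hazard 0.0350 × 0.643 = 0.0225.
- r(2) = (0.25/0.50) × 0.965 = 0.483; hazard 0.0350 × 0.483 = 0.0169.
- Month-12 estimate: 1 − (0.9775 × 0.9831) = 3.9%, about 43% below 6.89%. Simulation gave 3.89%.

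**Other follow-up assumptions** (nominal visits, no mTEC confirmation, simulated)

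| Months of follow-up | Share reaching M6 / M12 / M18 | Month-12 estimate | Shortfall against 6.89% |
|---|---|---|---|
| Uniform 1.5–21.8 | 0.751 / 0.449 / 0.169 | 3.38% | 51% |
| Uniform 1.5–18 | 0.703 / 0.339 / 0 | 1.70% | 75% |
| Uniform 1.5–15 | 0.643 / 0.207 / 0 | 1.10% | 84% |
| Accelerating recruitment, 1.5–21.8 | 0.586 / 0.217 / 0.032 | 1.77% | 74% |

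Putting the shares into the formula reproduces each row. For the first: 0.0350 × 0.449/0.751 = 0.0209 and 0.0350 × 0.169/0.449 = 0.0132, giving 3.4%.

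**What makes it smaller**
- *mTEC.* If everyone attended mTEC before the cut-off and it counted as a confirming visit, the month-12 estimates were 6.0% to 6.4%. That is 19 to 36% below the all-diagnoses curve in the same runs (7.8% to 9.4%, itself raised by the irregular extra visit), or 7 to 13% below 6.89%. With half attending, the shortfall against the all-diagnoses curve was 31 to 55%.
- *Visit window.* With visits spread over the ±4 weeks of Protocol Section 6 and actual dates used, the current rule gave 4.7% to 5.2% for follow-up of 0–21 or 0–24 months, read at the end of the month-12 window. That is 25 to 32% below 6.9%.

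**Planned design.** Under five to seven years of follow-up, the same rule gives 28.5% against 30.0% at month 60 (5% low) and 31.3% against 34.8% at month 72 (10% low).

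**The alternative rule.** If non-events leave the risk set after the last visit that another assessment followed, nominal visits give 3.49% and 6.88% at months 6 and 12 (uniform 1.5–21.8), against 3.50% and 6.89%. Month 18 cannot be estimated in that case. On actual dates the same censoring overshoots to 16% or more by the end of the month-12 window, because participants leave the risk set part-way through a visit window.

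**The case against.** **Size.** A reader might infer that the reported rates are about half the truth, or that half is the worst case. The documents support neither. They give no follow-up distribution, and the shortfall moves from about 10% to about 85% with the assumption made.

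**mTEC.** Protocol Table 6-1, footnote 42, brings ongoing participants in at their next scheduled visit, so some may have had a confirming assessment before 25 August 2019. Others would have been seen after it, and Protocol 8.5 applies the adjudication charter only until treatment termination. This stands as a real uncertainty about size.

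**Mitigation.** SAP 2.5.3 and 2.5.4 add counts of investigator diagnosis changes, CDR global increases and adjudication results regardless of confirmation, plus a Kaplan-Meier for first change in diagnosis classification. These help the reader. They are different endpoints with a different cut-off (database lock), however, and they do not correct the confirmed-event curve.

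**Consequence.** Inferential analyses have been dropped. At the five-event minimum, an exact Poisson 95% interval for the count runs from about 1.6 to 11.7, so a twofold shift lies within sampling error. That limits the importance of the point. It does not make the estimate unbiased.

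**Unseen detail.** SAP 2.5.5 defers further derivation rules to the programming specifications, which could contain something relevant.

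**Conclusion.** The mechanism and its direction follow from SAP 2.5.3 to 2.5.5, and nothing in the SAP text corrects them. The per-arm confirmed-event probabilities and their intervals are biased downward, by roughly 10% to 85% at month 12 across the assumptions tried. The low end needs full mTEC attendance with valid confirmation. The high end needs follow-up that rarely reaches 18 months. All figures assume exponential onset, diagnosis at the next visit, and attendance unrelated to diagnosis.

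A reader might go further and infer that the treatment comparison is distorted. The documents do not support that: the rule is the same in every arm and, with similar follow-up, acts alike in each. The outputs for first change in diagnosis classification and for RBANS decrease do not use confirmation and are outside this point. It is worth correcting because the curve is presented for the primary endpoint, but it affects description only.

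**What to change.** 1. Add a confirmed-event Kaplan-Meier or life table on nominal visits, using the windows of SAP Table 5-12. Each non-event leaves the risk set after the last visit that was followed by another diagnosis assessment before the cut-off, or at randomisation if there is none. Mark later times as not estimable. Do not apply this censoring to actual assessment dates, because that overestimates the rate.
2. Show the current rule's curve beside it, labelled as biased downward.
3. Report by arm the number with fewer than two post-baseline diagnosis assessments and the number of diagnoses pending confirmation at the cut-off. State whether mTEC assessments could confirm.

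The programming cost is one derivation, one rerun and a footnote. The statistical cost is larger: anyone followed for under 12 months contributes no risk time, which is 12/24 = 50% or 12/21 = 57% of participants under uniform follow-up of 0–24 or 0–21 months, before drop-out, so precision falls. The added analysis also assumes that newly diagnosed participants return as often as others. It would come after database lock and should be labelled post hoc.

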2.5.4 Statistical hypothesis, model, and method of analysis

Except from the primary objective on the TTE endpoint, the other primary objective (for APCC) aimed to evaluate effects of CNP520 versus Placebo by comparing changes from baseline to Month 60. Due to the early termination of CNP520, no data have been collected at Month 60. Only very few participants have provided data on active treatment with CNP520 beyond one year of follow-up. Hence, the originally planned inferential and model based statistical analyses cannot be performed and are no longer applicable.

Time to event (MCI due to AD or dementia due to AD), Time to first change in diagnosis classification and Time to first decrease in RBANS Total of ≥ 14 points

Tables

Time to Event analysis using Kaplan Meier approach will be presented for time to MCI due to AD or Dementia due to AD (events as per protocol) and for time to first change in diagnosis classification (this is an event regardless of confirmation and adjudication) from cognitively unimpaired by the investigator. Analysis of time to first change in diagnosis classification will also be performed for participants on treatment. In addition, analysis of time to first decrease in RBANS Total Score of ≥ 14 points will be performed for participants on treatment (for on treatment definition, refer [Section 2.1.1](#)). The Kaplan-Meier estimates of the cumulative event rate for each treatment group will be summarized and plotted. To calculate the proportion of participants with events, number of participants at risk will be used as the denominator. "Participant at risk" at a specific time point is defined as the number of participants in the study without an event at up to that time point.

These analyses will only be performed if there are at least five such events.

In addition, the number and percentage of the additional situations ([Section 2.5.3](#)) defined events overall (not by visit) will be summarized by treatment group.

APCC score

Tables

The APCC test score and the seven components (listed above in [Section 2.5.3](#)) will be summarized on the SAF.

